## ***Statistical analysis plan***

Sample size determination. Sample size is based on statistical power analyses for the primary hypothesis based on single primary outcome (opioid abstinence without MOUD). A conservative approach was used to preserve power with a smaller effect size than observed from prior uncontrolled, non-blinded intervention studies with the NET Device. Power analyses examined sample sizes required to detect clinically meaningful group differences between sham and active groups. This represents standardized difference between the two groups after adjusting for the effect of the covariate “duration of inpatient residence” (which is capped at 28 days). Sample size determination was carried out *via* simulation in R-software; 5000 iterations were run in which group means were generated using a mixed-effect additive model. Sample size is a function of hypothesized effect size (standardized group difference) and the sign and magnitude of the regression coefficient (duration of inpatient residence). With projected N=100 (enrolled) there will be sufficient power to detect a standardized effect size of 0.45 or higher.

Missing data. In this ITT design, a participant is “included” (becomes part of the evaluable ITT data set) when he/she completes 1-hr of device use. We expect only 5% attrition, i.e. for 100 participants who complete 1-hr of device use, we expect to consent 105 individuals. A comparable trial of a

percutaneous electrical stimulation device for treating opioid withdrawal symptoms found that 71 of 73 enrolled participants completed 1-hr of device use, only 2.8% attrition [18]. **Table 1** explains how missing data are handled, i.e. for the primary efficacy endpoint, missing data are imputed as “not opioid abstinent without MOUD”. The definition of the primary endpoint (“opioid abstinence without MOUD”) and secondary endpoint (“non-opioid abstinence”) thus covers any intermittent missing values and loss to follow-up, and is not expected to impact power of the primary analysis. Premature study termination (e.g., death, relocation, or adverse events) may result in missing data, although this attrition is expected to be low. The projected sample size (N=125) was increased to cover unforeseen events.

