Participant withdrawal. Participants can withdraw from the study at any time on request. Discontinuation of device use prior to completing the minimum 1-hr treatment period constitutes withdrawal from the study. The investigator may discontinue or withdraw a participant from the study for the following reasons: (1) significant study intervention non-compliance; (2) if any clinical adverse event (AE), laboratory abnormality, or other medical condition or situation occurs such that continued participation in the study is not in the best interest of the participant; (3) disease progression which requires discontinuation of the study intervention; (4) if the participant meets an exclusion criterion (either newly developed or not previously recognized) that precludes further study participation; or (5) participant is unable to receive treatment following enrollment.

Participants who sign the informed consent form and are randomized but do not receive the study intervention will be replaced. Participants who sign the informed consent form, are randomized, receive the study intervention, and subsequently withdraw or are withdrawn, will be replaced.

Participants who withdraw from the study will receive TAU as defined by treatment staff (who are independent of the research staff), where such care may include MOUD.

Lost to follow-up. A participant is considered lost to follow-up if s/he becomes unavailable for all video assessments following discharge from the inpatient environment.

Populations for analysis. The ITT analysis dataset and the safety analysis dataset will contain all randomized participants. The per-protocol analysis dataset will contain the subset of the ITT dataset who: (1) present with a COWS score of moderate or above; (2) receive at least 1 hr treatment from the device; and (3) complete at least one post-discharge video interview.

Efficacy endpoints. The primary analysis will assume that data came from a mixed-effect linear model. Each model will include a random intercept, fixed effect for treatment, participant-specific random effect and covariate corresponding to duration of inpatient residence. The primary hypothesis involves testing the main effect for treatment difference between the groups (sham vs. active). A likelihood ratio test will examine the group effect focusing on the primary hypothesis.

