h = illicit opioid (e.g., heroin) drug screen or self-report is positivem = medication for opioid use disorder (MOUD) or self-report is positive

'-' = missing value

Cases measuring “abstinence without MOUD”:

Heroin use, no MOUD {1,1,1,h,h,1,1,1,1,1,h} = 9/12

Heroin use, no MOUD, missing weeks {1,1,1,h,h,1,--,1,1,--,} = 6/12

MOUD use, no Heroin {1,1,m,m,m,m,1,1,1,1,1} = 8/12

MOUD use, no Heroin, missing weeks {1,1,m,m,m,m,1,1,--,} = 4/12

[figure not shown]
Heroin use, MOUD use {1,1,h,h,h+m,m,m,m,m,h,1,1} = 4/12

Heroin use, MOUD use, missing weeks {1,1,h,h,h+m,m,--,m,h,--,} = 2/12

[figure not shown]
**Table 2.** Participant selection criteria

Inclusion Criteria	Exclusion Criteria

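### The investigator may withdraw a participant from the study, not only from the device, and nothing in the plan continues outcome collection for those withdrawn

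*Combined protocol and SAP*

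**What the plan says.** All of the following is in the combined protocol and SAP.

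- **Statistical analysis plan, Participant withdrawal.** The clause acts on study participation: "The investigator may discontinue or withdraw a participant from the study for the following reasons: (1) significant study intervention non-compliance". Ground (3) is "disease progression which requires discontinuation of the study intervention". Ground (4) applies "if the participant meets an exclusion criterion (either newly developed or not previously recognized) that precludes further study participation". Ground (2) covers adverse events and medical situations in which staying in the study is against the participant's interest. Ground (5) is inability to receive treatment after enrolment. Treated participants who leave, "and subsequently withdraw or are withdrawn, will be replaced". Those who withdraw receive usual care from staff independent of the research team. Nothing is said about their study assessments.
- **Populations for analysis.** "The ITT analysis dataset and the safety analysis dataset will contain all randomized participants".
- **Missing data.** A participant joins the evaluable ITT set only on completing 1 hour of device use. The same paragraph says that "for the primary efficacy endpoint, missing data are imputed as" not abstinent. It also says: "Premature study termination (e.g., death, relocation, or adverse events) may result in missing data", and expects little of it.
- **Table 1.** Missing weeks stay in a denominator of 12. The row "MOUD use, no Heroin, missing weeks" is scored 4/12.
- **Study design; Participant selection criteria.** Participants may stop the device whenever they wish. One hour of use starts the follow-up assessments. Stopping stimulation and dropping out of the study are named as two different events.

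**The concern.** An ITT comparison of 12-week abstinence needs outcomes after the device has stopped, whatever the reason for stopping. Device use lasts at most 7 days and the primary endpoint covers the 12 outpatient weeks, so for everyone most of the endpoint is measured off the device. Grounds (1) and (3) are reasons to stop a device, yet as written they can end study participation. Ground (4) can do the same.

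The outcomes lost this way are lost through an investigator's decision, not through relapse or lost contact. They could still be collected, because the weekly video calls and 12 test kits per participant are already planned. If such withdrawals differ by arm, the primary comparison is biased. If they do not, scoring the lost weeks as failures still dilutes a true difference. The text also leaves open whether those weeks count as failures or the participant is swapped out, and these two treatments push the estimate in opposite directions.

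**Working it through.** **1. How the lost weeks would be scored.** The check is to count the weeks coded 1 in the three Table 1 rows with missing weeks and divide by 12. This gives 6/12, 4/12 and 2/12, which are the plan's own figures, so missing weeks score 0 and stay in the denominator. Applied to an investigator withdrawal after 1 hour of use:
- withdrawn before discharge: 0/12, whatever happens later;
- withdrawn after four abstinent outpatient weeks: 4/12, whatever happens later.

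This is the likelier reading, since Populations for analysis keeps all randomised participants. The replacement sentence leaves a second reading open, in which the participant leaves the data set. For a removal before 1 hour, Populations for analysis includes the participant and Missing data does not.

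**2. Scale.** The pilot SDs of 1.19 and 3.46 weeks and the design effect of 0.45 come from Expected outcomes; 50 per arm comes from Study design.
- Equal-weight pooled SD = sqrt((1.19² + 3.46²)/2) = 2.587 weeks.
- Design difference = 0.45 × 2.587 = 1.164 weeks.
- One withdrawn participant moves an arm mean by at most 12/50 = 0.24 weeks.

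The documents give no withdrawal rate, so every share below is an assumption. Removal is taken to occur before discharge.

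**3. Balanced removal, scored as failure.** With a share p = 0.10 removed from each arm:
- removal unrelated to abstinence: 1.164 × (1 − p) = 1.164 × 0.90 = 1.05 weeks;
- removed participants would have had half the abstinence of the others: 1.164 × (1 − p)/(1 − p/2) = 1.164 × 0.90/0.95 = 1.10 weeks.

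**4. Unbalanced removal with no true effect.** Both arms have the same true mean m. If scored as failure, the false difference is m × (difference in p) when removal is unrelated, or m × the difference in (1 − p)/(1 − p/2) under half-abstinence. With m = 3.97 (pilot active mean) and 5% of active against 10% of sham removed:
- unrelated: 3.97 × 0.05 = +0.20 weeks;
- half-abstinence: 3.97 × (0.95/0.975 − 0.90/0.95) = +0.11 weeks.

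False-positive rates were simulated with 40,000 trials per scenario, 50 per arm, beta-binomial weeks out of 12 matched to the pilot mean and SD, and a two-sided 0.05 t-test without covariate. The plan states no alpha.

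| Removed, active v sham | True mean in both arms | Half-abstinence | Unrelated |
|---|---|---|---|
| 10% v 10% | 3.97 | 5% | 5% |
| 5% v 10% | 3.97 | 5% | 6% |
| 10% v 20% | 3.97 | 6% | 9% |
| 10% v 20% | 0.48 | 5% | 5% |

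**5. Scored as failure against left out.** Take 10% v 20% removed, mean 3.97, half-abstinence.
- Scored as failure: 3.97 × (0.90/0.95 − 0.80/0.90) = +0.23 weeks.
- Left out: 3.97 × (1/0.95 − 1/0.90) = −0.23 weeks.
- Gap: 0.46 weeks, or 0.464/1.164 = 40% of the design difference. At mean 0.48 the gap is 0.056/1.164 = 5%.

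**The case against.** **Reach.** Grounds (1), (3) and (5) concern the device or its receipt, so they arise mainly within the device window of at most 7 days. After 1 hour, non-compliance has little to act on, because participants may stop at will. Ground (2) is close to a safety exception that any plan would keep. All of this stands, and it limits how often the clause would bite. It does not alter what happens to someone withdrawn in week 1: all 12 outpatient weeks are then lost.

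**Pre-specified scoring.** Missing counts as failure by an explicit rule, early termination is named as a source of missing data, and the projected sample was raised to 125 for unforeseen events. With balanced removal the rule works against the device. That too stands. But the rule is conservative only if removal is balanced or heavier in the active arm, and extra participants do not recover the outcomes of those removed. The expected 5% attrition concerns reaching 1 hour of use, so it does not bound later withdrawal.

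**Stronger readings that the documents do not support.**
- *Everyone who stops the device is lost.* Study design and Participant selection criteria separate stopping the device from leaving the study. The gap is confined to withdrawal by the investigator.
- *The clause favours the device or seriously inflates the false-positive rate.* In the same simulation at mean 3.97, 10% v 30% or 40% removed gives 11% or 19% (half-abstinence) and 21% or 41% (unrelated). No document suggests such imbalance. The principal investigator and staff are blinded, so an imbalance would have to arise through symptoms or perceived benefit, which makes unrelated removal the less natural assumption. At the pilot sham mean of 0.48 the same shares give 5% or 7%, and 7% or 11%. The planned model also adjusts for inpatient stay, which the t-test does not.
- *Starting an excluded medicine as an outpatient ends participation.* Ground (4) is discretionary and applies only where the criterion rules out continuing. The documents give no such case.

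**Conclusion.** The concern holds as a gap in the withdrawal clause. Grounds (1), (3) and (4) can end study participation, treated participants who are withdrawn are replaced, and no text keeps collecting their outcomes. Following the plan as written would discard data that the trial is already equipped to obtain.

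For those past 1 hour of use, failure scoring is the likelier treatment, but omission is not ruled out. Before 1 hour, the two ITT definitions conflict. The direction and size of bias cannot be determined. Under the assumptions above, 10% balanced removal costs 0.06 to 0.12 weeks of a 1.16-week difference, and small imbalances leave the false-positive rate near 5%. The case for acting is that outcome collection and scoring should be settled before unblinding and that the remedy is cheap. It does not rest on any demonstrated large bias.

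**What to change.** 1. In Participant withdrawal, state that after randomisation grounds (1), (3) and (4) stop the device but not follow-up, and that ground (2) ends follow-up only if continued contact is unsafe. Participants may still withdraw consent.
2. Continue the planned weekly video call, timeline follow-back and oral fluid test to outpatient week 12, and score observed weeks as observed.
3. Keep these participants in the ITT set and delete the replacement of treated participants.
4. Align the ITT definition under Missing data with the all-randomised definition under Populations for analysis. One hour of use is already a per-protocol condition and can stay there.
5. Report investigator withdrawals by arm and ground. A sensitivity analysis that multiply imputes weeks still missing because of an investigator withdrawal is optional.

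The cost is wording and slightly more follow-up calls. The calls and the 12 kits plus one spare per participant are already planned, no extra participants are needed, and there would be fewer replacements. Whether a given condition or medicine requires the device to stop remains a clinical decision.

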### ***Outcome measures***

During the 12-week outpatient period, participants will be interviewed for safety and efficacy endpoints and undergo a remote drug screen. Remote interviews reduce risk of COVID-19 exposure for the participant and research assistant, and decrease transportation barriers (increased feasibility). Each week, the research assistant hosts a live video call with the participant, and conducts a timeline follow-back (TLFB) review of opioid, MOUD, stimulant, sedative, cannabis and alcohol use for each of the prior 7 days. At discharge from the inpatient facility, each participant will be given 12 kits (plus

one spare) of the Premier Biotech OralTox OT-80605, an FDA 510(K) cleared 6-panel rapid oral fluid drug screen. Each test covers amphetamines and methamphetamine (positive cutoffs = 50 ng/ml), opioids and THC (positive cutoffs = 40 ng/ml), oxycodone and cocaine (positive cutoffs = 20 ng/ml). Each individually packaged test is sealed in foil and is marked with a lot number and expiration date. Each individual test contains a QR code that encodes a unique identification number that will be used to validate authenticity and uniqueness of the screen. The participant receives printed and verbal instructions for use from the research assistant, is observed during each test, and test results with authenticating QR code are captured as an image file by the research assistant and saved for validation. In order to conduct this FDA-qualifying study during the COVID-19 pandemic, remote test methods were evaluated for use during the outpatient phase. When this study began, FDA had only approved a limited selection of oral fluid rapid tests for use in research. The authors selected TLFB self-report as the primary source for data, supplemented by such relevant oral fluid tests as were FDA approved.

The primary efficacy endpoint is each participant's overall percentage of weekly abstinence from illicit opioid use without use of MOUD. This is defined as the percentage of each participant's negative oral fluid samples and self-reports of illicit opioid, methadone, buprenorphine, and naltrexone use per week throughout the 12-week outpatient study period. The rationale for choosing this endpoint is to perform a rigorous test of the isolated efficacy of NET, with the safety net of allowing (and measuring) participants' use of MOUDs.

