During a given week, oral fluid samples and self/pharmacy reports that both indicate no illicit opioid, methadone, buprenorphine, or naltrexone use will be considered "opioid-abstinence without MOUD". Cumulative distribution function, time (days) to first use of illicit opioids, time (days) to first use of MOUD, and duration (weeks) of continuous abstinence without MOUD will be evaluated as supportive outcomes. Response profiles for each treatment arm are based on each participant's individual rates of weekly illicit opioid or MOUD use, including negative oral fluid results and daily

self (TLFB) of illicit opioid or MOUD use/non-use. **Table 1** presents explanatory cases of the primary efficacy endpoint measurement. The null hypothesis is that “opioid abstinence without MOUD” will not significantly differ between active and sham groups, whereas the alternative hypothesis is that “opioid abstinence without MOUD” will be superior in the active (relative to sham) treatment arm.

The secondary efficacy endpoint is each participant’s percentage of non-opioid drug-free weeks during the 12-week outpatient period. Non-opioids assessed include cocaine, sedatives, and stimulants. Use of alcohol and cannabis will be measured, but are not included in the secondary efficacy analysis, due to their legal status. Response profiles for each arm are based on each participant’s individual rates of weekly abstinence data, including negative oral fluid results and daily self-reports of non-opioid drug use/non-use (TLFB).

The secondary safety endpoint is the prevalence of all adverse events (AEs), serious adverse events (SAEs), adverse device effects (ADEs), serious adverse device effects (SADEs), unanticipated adverse device effects (UADEs), and device deficiencies.

Supportive and exploratory measures. Treatment retention will be measured throughout the inpatient and outpatient phases. Self-stimulation intensity (in 5-min bins), duration, and device on/off data from each NET Device are automatically transmitted to a computer server and processed offline. Opioid withdrawal symptoms, craving severity, and positive/negative affect are measured daily during the first inpatient week. Measures of depression, anxiety and stress, sleepiness, and health-related quality of life are obtained at the conclusion of inpatient and outpatient phases.

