### ***Participant selection criteria***

Screening includes informed consent, HIPAA authorization, assessment of demographics, contact data, pregnancy testing, contraception methods, medical history, and urine drug testing (including fentanyl, buprenorphine, and methadone). Assessments are aligned with the treatment

facility's standard of care such that electronic case report forms (eCRFs) can be rapidly reviewed for study eligibility by the remote investigator, given the time-sensitive nature of enrollment.

During the recruitment and informed consent process, participants are repeatedly told they can receive FDA-approved MOUD at the treatment facility instead of participating in the study. They are also told that upon discontinuation of device stimulation, and/or if they drop out of the study, they can receive TAU (including MOUD) at any time. All participants are given a "loss-of-opioid tolerance" warning (i.e. stopping opioids leads to reduced tolerance, and subsequent opioid use increases their risk of overdose and death), which they must sign. Participants are also given a naloxone kit upon discharge from the treatment facility and educated on its use. All of these procedures are documented in the medical record and case report forms.

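### The plan describes no way to learn of overdose or death in participants who stop attending the weekly call, and its lost-to-follow-up rule, read literally, does not count them

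*Combined protocol and SAP*

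**What the plan says.** Under Participant selection criteria, every participant signs a warning that, once tolerance is lost, "subsequent opioid use increases their risk of overdose and death".

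For the outpatient phase, Outcome measures states: "During the 12-week outpatient period, participants will be interviewed for safety and efficacy endpoints and undergo a remote drug screen". The contact is weekly: "Each week, the research assistant hosts a live video call with the participant". The Schedule of Activities (Figure 3) lists adverse events at the inpatient assessments and at these outpatient contacts.

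In the Statistical analysis plan, the lost-to-follow-up paragraph reads: "A participant is considered lost to follow-up if s/he becomes unavailable for all video assessments following discharge from the inpatient environment". The third per-protocol criterion is its mirror image: participants must "complete at least one post-discharge video interview".

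On the safety result, Outcome measures says "The secondary safety endpoint is the prevalence of all adverse events (AEs), serious adverse events (SAEs", and the list continues through device effects and device deficiencies. Overdose and death are not itemised. The population is stated as "The ITT analysis dataset and the safety analysis dataset will contain all randomized participants". The analysis is descriptive only.

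The missing-data paragraph foresees that "Premature study termination (e.g., death, relocation, or adverse events) may result in missing data", without saying how a death would become known. Missing weeks are scored as not abstinent for the primary endpoint. There is no corresponding statement for safety.

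**The concern.** A participant who has died cannot report it on a video call, and one who is in hospital or has relapsed heavily may not attend. The events the plan itself warns about are thus among those most likely to end attendance at the one outpatient contact where safety data are collected. If nothing else is done, a person who never returns contributes to the denominator of the safety prevalence but can contribute no later event to the numerator.

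The lost-to-follow-up rule adds a second problem. On its literal reading it reports as lost only those who attended no call at all, so the reported number would not tell a reader how much outpatient time went unobserved.

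At stake is how far the outpatient safety table can be trusted on overdose and death, in a trial whose participants start without MOUD and which, under Data & safety monitoring, has no safety monitoring board.

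**Working it through.** The plan gives no outpatient dropout rate and no event rate, so there is no stated figure to reproduce. The check has two parts.

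**Reading the sections together**

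1. Denominator: all randomized participants (Populations for analysis).
2. Numerator: events that become known. The described outpatient route is the interview (Outcome measures, Figure 3).
3. Rule for participants whose status is unknown, or for exposure time: none given (Safety endpoints paragraph).
4. Procedure for people who stop attending or withdraw: no vital-status check, record search or re-contact step is described. Contact data are collected (Participant selection criteria, Figure 3) but are not tied to safety. Pharmacy reports are mentioned only for the abstinence endpoint.
5. Label: zero calls attended means lost; one call attended means not lost, on the literal reading. The per-protocol criterion of at least one interview supports that reading.

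Followed as written, points 1 to 3 treat a participant who never returns as event-free from the last contact onward.

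**Arithmetic on observed time**

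Input from the plan: 12 weekly outpatient calls. Someone seen only at call 1 has 11/12 = 91.7% of the outpatient window unobserved.

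Let f be the fraction who vanish after call 1, and k the event rate in unobserved time divided by that in observed time. Both are assumptions. Assume also that no event is learned outside the call.

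- Unobserved share of person-time = f × 11/12.
- Share of events captured = (12(1−f) + f) / (12(1−f) + f + 11fk).

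| f | Unobserved person-time | Captured, k = 1 | Captured, k = 2 | Reported lost from this group |
|---|---|---|---|---|
| 10% | 9.2% | 10.9/12 = 91% | 10.9/13.1 = 83% | 0 |
| 30% | 27.5% | 8.7/12 = 72.5% | 8.7/15.3 = 57% | 0 |
| 50% | 45.8% | 6.5/12 = 54% | 6.5/17.5 = 37% | 0 |

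With 50 per arm, the middle row is 15 people and 15 × 11 = 165 of 600 person-weeks. For deaths the formula is generous: it counts an event in observed time as captured, yet a death between calls cannot be self-reported at the next one.

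Effect on a comparison: with equal true rates, k = 1, and 20% of active and 40% of sham participants vanishing (assumed), the apparent active-to-sham ratio is (12 × 0.8 + 0.2)/(12 × 0.6 + 0.4) = 9.8/7.6 = 1.29. Swapping the two fractions inverts it.

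Effect on a zero count: the one-sided 95% upper limit is 1 − 0.05^(1/n). With n = 50 all of known status it is 5.8%. With 30 of known status (assumed) it is 9.5%.

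**The case against.** The strongest reply is that the lost-to-follow-up label drives no analysis. The safety set is everyone randomized and missing weeks are imputed whatever the label, so rewording it would recover no event. That stands: any undercount would come from the absent ascertainment procedure, and the label only affects how visible the incomplete follow-up is.

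Several stronger readings also fail.

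- A reader might infer that overdose and death can be learned only from the call. The documents are silent on other routes but do not exclude them. The missing-data paragraph presupposes that a death can become known.
- A reader might infer that someone who vanishes after week 1 counts as retained. Outcome measures plans a separate retention measure through both phases, and Table 1 shows missing weeks kept per participant. The disappearance would be in the data, though not in the lost-to-follow-up count or the described safety summary.
- A reader might treat every missed week as unobserved for safety. A participant who returns can report a non-fatal event at the next call. The gap concerns those who never return.
- A reader might take the pilot means as showing how common the risk is. Non-abstinent weeks under the plan's definition mix illicit use, MOUD use and missing data.

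The rule is also ambiguous: it can be read as covering all remaining calls. The per-protocol criterion favours the literal reading but does not settle it, and the wording needs repair either way.

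What survives is that neither section on safety tells anyone to find out what happened to a participant who does not come back, or tells the reader how many such participants there are.

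**Conclusion.** The point holds as a gap in safety ascertainment and reporting. The plan names overdose and death as the risk, describes no route to them in participants who stop attending, and reports safety over all randomized participants without separating event-free from unknown. Its lost-to-follow-up rule, on the literal reading, leaves out a participant with 11 of 12 weeks unobserved.

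Outpatient events may be undercounted, by an amount that depends on retention in each arm. It would go too far to say that they are undercounted or that the serious adverse event prevalence is wrong: the captured shares of 37% to 91% in the table rest on assumed values of f and k and on no event being learned elsewhere. Nor do the documents show that the device would look safer than it is. The arm that keeps more participants shows more of its events, and if that were the active arm it would look less safe. Size and direction remain unknown, which is the reason to collect and report the missing information. The change is worth making because it is cheap.

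**What to change.** 1. Define lost to follow-up as status not obtainable at outpatient week 12, with the date of last contact recorded, and report it by arm. Alone, this recovers no events.
2. At the end of week 16 of the schedule (outpatient week 12), have existing staff use the contact data already collected to record vital status (alive, dead or unknown) and any overdose or hospital admission. Do this for all randomized participants, to match the plan's safety set, including withdrawn and replaced participants who have not refused contact. This is the step that recovers events.
3. Report deaths, overdoses and serious adverse events by arm in all randomized participants, next to the number with known status and the observed outpatient person-time.

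Cost: protocol and analysis-plan wording, one eCRF page and some phone time, with no new visit or staff. Consent wording may be needed to permit the status check; the consent pages were not available for review. The loss-to-follow-up and serious adverse event figures may come out less favourable than under the present wording.
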